### **3.4. Randomization**

Participants will be randomized 1:1 to dPEP versus standard of care; randomization will be done in variable- sized blocks and using a computer based randomization system, Randomize.net, following consent and eligibility confirmation.

### **3.5. Clinical Assessments**

Safety assessments are limited to the following:

In dPEP arm only:

- All grade 2 and higher AEs that are judged related to dPEP, in the opinion of the site clinician, that result in an interruption of study drug
- All grade 3 and 4 adverse events judged to be related to doxycycline

In both arms:

- All AEs meeting SAE definition regardless of relationship with dPEP

In this open label trial, for those randomized to receive doxycycline PEP, all AE's and SAE's have attribution recorded as doxycycline-related or not doxycycline-related, in the judgment of the site investigator.

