## 6.0 ADVERSE EVENTS (AE) AND STUDY MONITORING

### **Adverse Event Collection Requirements**

The following AEs will be recorded on data collection forms:

- All AEs that are attributed to doxycycline in the opinion of the site investigator
- All AEs meeting SAE definition

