### **2.2.3. Safety, tolerability and acceptability of dPEP**

- Safety:
  - serious adverse events (SAEs),
  - all related AEs (assessed in the dPEP arm only)
- Tolerability:
  - dPEP discontinuation (assessed in the dPEP arm only)
  - Candida yeast infection treatment (documented as fluconazole on STI treatment CRF)
  - Doxycycline-specific side effects (assessed via standardized symptom assessment: includes reports of nausea, pill esophagitis, photosensitivity)
- Acceptability:
  - Acceptability and Optimism questionnaire (FDAO) (13 question on a 5-point Likert scale)

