### **8.1. Adverse Events and Deaths**

#### **8.1.1. AE Definitions**

The following AEs are recorded on eCRFs:

- All SAEs
- All AEs attributed to doxycycline in the opinion of the site investigator

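### SAP 3.5 narrows the doxycycline-related adverse events to be assessed, contradicting SAP 2.2.3, SAP 8.1.1 and the protocol, which cover related events of every grade

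*SAP*

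**What the plan says.** SAP 3.5 opens its list with "Safety assessments are limited to the following". For the dPEP arm the list has two entries. The first is "All grade 2 and higher AEs that are judged related to dPEP", subject to the further condition "that result in an interruption of study drug". The second is "All grade 3 and 4 adverse events judged to be related to doxycycline". For both arms it adds "All AEs meeting SAE definition regardless of relationship with dPEP".

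Elsewhere the scope is wider:

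- SAP 2.2.3 gives the safety endpoint as "all related AEs (assessed in the dPEP arm only".
- SAP 8.1.1, headed AE Definitions, lists what goes on the eCRFs: SAEs and "All AEs attributed to doxycycline in the opinion of the site investigator".
- Protocol 6.0, Adverse Event Collection Requirements, sets the same recording rule: "All AEs that are attributed to doxycycline in the opinion of the site investigator", plus SAEs.
- Protocol 10.0, under secondary outcomes, also names all related AEs, in the dPEP arm only.

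SAP 8.1.2 then tabulates related AEs by grade for the dPEP arm.

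**The concern.** The opening words of SAP 3.5 are exclusive, so its list cannot be read as a highlighted subset of a wider collection. Both scopes stand in the current SAP, and the narrower one also departs from the protocol.

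What is at stake is the by-grade table of related AEs. A table of all related AEs needs a grade 1 row and a complete grade 2 row, and only the wider rule fills them. If the narrower rule were followed, a reader could not tell whether an empty grade 1 row meant that no events occurred or that none were collected. Safety and tolerability belong to objective 2, which both documents list as primary, although Protocol 10.0 places the safety measures among the secondary outcomes.

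**Working it through.** The plan gives no figure to reproduce, so the check sets the rules side by side. Each class of doxycycline-related AE in the dPEP arm is tested against both.

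| Related AE, dPEP arm | SAP 3.5 | SAP 2.2.3, SAP 8.1.1, Protocol 6.0 and 10.0 |
|---|---|---|
| Serious, any grade | in (as an SAE) | in |
| Non-serious, grade 3 or 4 | in | in |
| Non-serious, grade 2, drug interrupted | in | in |
| Non-serious, grade 2, drug not interrupted | **out** | in |
| Non-serious, grade 1, interrupted or not | **out** | in |

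The rules differ in the last two rows only. Neither row can be assumed empty. Protocol 8.0 (Toxicity) allows a participant with related grade 1 or 2 toxicity to stay on drug, so grade 2 events without interruption are foreseen.

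**Size.** Let *s* be the grade 1 share of non-serious grade 1–2 related AEs, and *i* the probability that a grade 2 event interrupts drug. The share excluded by SAP 3.5 is

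*s* + (1 − *s*)(1 − *i*) = 1 − (1 − *s*)·*i*.

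The documents give neither *s* nor *i*. In principle the result runs from 0 (*s* = 0, *i* = 1) to 1 (*s* = 1). Purely as an illustration, assumed values of *s* = 0.3 and *i* = 0.5 give 1 − 0.7 × 0.5 = 0.65, and *s* = 0.8 and *i* = 0.1 give 1 − 0.2 × 0.1 = 0.98. The share falls below one half only when (1 − *s*)·*i* exceeds 0.5, which needs both *s* < 0.5 and *i* > 0.5. These are assumptions, and the conclusion does not rest on them.

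**Closing sentence of SAP 3.5.** It says that all AEs and SAEs in the dPEP arm have attribution recorded as related or unrelated. The list above it admits no unrelated event other than an SAE, so this sentence also needs reconciling.

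**The case against.** The strongest reply is that the wider rule plainly governs. The protocol sets what is collected, SAP 8.1.1 repeats it for the eCRFs, and SAP 8.1.2 follows directly under the same heading, so the natural reading is that 8.1.1 defines the table's contents. SAP 3.5 is the lone outlier and sits in the study design chapter. Nor does its list describe the whole safety and tolerability plan: it omits the symptom assessment, dPEP discontinuation and fluconazole-treated yeast infection, all of which are in SAP 2.2.3. This stands, and it makes the loss conditional. It does not remove the contradiction, because SAP 3.5 still states an exclusive and narrower rule.

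A reader might go further and infer that most low-grade events will be lost and that dPEP will look safer than it is. The documents do not support that, for four reasons:

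- Nothing shows that sites applied the narrower rule.
- No grade mix or interruption rate is given, so the word *most* has no documentary basis.
- Both arms are asked at each visit about doxycycline-type symptoms (protocol, General symptom assessment), and SAP 8.3 tabulates these by arm, along with doses not taken because of side effects. SAP 8.1.3 lists discontinuations due to AEs, and SAEs are collected in both arms under either rule.
- The related-AE table covers the dPEP arm only, and SAP 8 plans no between-arm AE tests, so no comparative AE estimate is distorted.

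These safeguards are partial. Symptom reports and discontinuation listings are not graded AEs with an attribution, and cannot fill the missing rows of the SAP 8.1.2 table.

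**Conclusion.** SAP 3.5 is wrong as written: it is inconsistent with two other SAP sections and with the protocol. The certain consequence, if it were applied, is that two classes of event would be missing from the table reported for the endpoint of all related AEs: every non-serious grade 1 related AE, and every non-serious grade 2 related AE without interruption. The number of events cannot be derived from the documents. If sites followed the protocol and SAP 8.1.1, nothing is lost and only the wording needs correction. The risk is an incomplete graded, attributed AE table in one arm, not a generally false safety picture. Severity is minor, and the efficacy analysis is unaffected.

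**What to change.** 1. In SAP 3.5, replace the two dPEP-arm entries with the recording rule of Protocol 6.0 (Adverse Event Collection Requirements) and SAP 8.1.1: all AEs attributed to doxycycline, of any grade, whether or not drug was interrupted.
2. Reword the closing sentence of SAP 3.5 so that the events it says carry an attribution match the events that are recorded.
3. Before database lock, check the AE form instructions to establish which rule the site used.
4. If only the narrower set was collected, document this as a departure from the protocol's collection rule, and relabel the SAP 2.2.3 endpoint and the SAP 8.1.2 table with the restriction stated. Relabelling alone would leave the departure unrecorded.

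The cost is a few lines of SAP text and one check of form instructions. No new analysis is needed, and SAP 1 already provides for the SAP to be finalized before lock. The change concerns recording and reporting only, not clinical management.

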## **4. PLANNED ANALYSES**

### **4.1. Interim Analyses**

The trial will be monitored by an independent data monitoring committee approximately every 6 months. The trial plans to continue until we have established definitive efficacy results, whether effective or ineffective, for both CT alone and for any STI. Two formal interim monitoring times are planned, when 1/3 and 2/3 of the follow-up visits have been completed, with stopping rules based on consideration of both the primary outcome and the CT outcome alone. Because the outcomes are highly correlated, no adjustment for multiple comparisons is planned. O'Brien-Fleming boundaries will be used, with stopping based on the alpha spending corresponding to observed p-values in the efficacy analyses. Stopping for both efficacy and lack of efficacy will be considered; however, a decision to stop for efficacy will need to balance the need for evidence assessing the potential harm of acquired tetracycline resistance.

### **4.2. Final Analyses**

The final analysis will be conducted after database lock of all final (12 month) study visits.

## **5. GENERAL CONSIDERATIONS FOR DATA ANALYSES AND HANDLING**

### **5.1. Data Presentation Conventions**

Continuous variables (e.g. age) are summarized using descriptive statistics (the number of subjects with available data, the mean, standard deviation (SD), median and minimum and maximum). Categorical variables (e.g. preferred language) are summarized using counts and percentages. Percentages are calculated using the total subjects per treatment group.

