## **5.3. Handling of Missing Data**

### **5.3.1. Missing Efficacy Endpoints**

Complete case analysis will be used for the primary efficacy analysis

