### **Descriptive analysis**

- The number of participants with any bacterial STI, and with each type of STI, will be summarized at each scheduled visit by arm
- The number of STIs reported by each participant will be summarized at each scheduled visit by arm. Detail of testing and results at interim visits will also be summarized.
- Occurrence and results of test of care visits will be summarized.

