### **Statistical analysis**

Comparison of STI incidence by arm will be conducted by estimating the relative risks of any STI over the 3, 6, 9 and 12 month visits using a modified Poisson model fitted using GEE methods to account for repeated observations from each participant, assuming an independent covariance structure, with study arm as the only covariate[1]. The test for significance will be a two-sided alpha = 0.05. 95% confidence intervals will be computed using robust standard errors.

The same analysis will be repeated for the individual STIs.

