### **7.7. Analysis of Tetracycline resistance**

#### **7.7.1. Analysis of TCN resistance in GC cases**

TCN resistance will be assessed in GC cases only. TCN resistant GC will be defined by the detection of plasmid-mediated *tetM* gene conferring high-level tetracycline resistance.

Descriptive statistics: Tabulations of resistance (No GC, GC: TNC resistance testing = missing, not resistant, resistant) will be reported at baseline, 3, 6, 9 and 12 month visits in GC cases in each arm.

Statistical analysis: Assessment of odds of resistance by arm will be assessed by estimating the odds of GC infection with resistance among cases detected after enrollment using logistic regression, adjusted for visit.

Sensitivity analysis: molecular chromosomal mutations may lead to expression of tetracycline resistance. Tabulations of number of expressed chromosomally-mediated tetracycline resistance determinants (*mtrR*, *rpsJ*, *porB*, and *pilQ*) will be reported at baseline, 3, 6, 9, and 12-

month visits in GC cases, among those with or without plasmid-mediated tetracycline resistance (i.e., detection of *tetM*), in each arm.

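### SAP 5.1 fixes the whole arm as the percentage denominator, so by-visit STI percentages and the control-arm doxycycline-detection percentage would count untested women as negative

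*SAP*

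**What the plan says.** SAP 5.1 states the general convention: "Categorical variables (e.g. preferred language) are summarized using counts and percentages", followed by "Percentages are calculated using the total subjects per treatment group". The same paragraph asks for the count of non-missing observations when a continuous variable is summarised, but asks for nothing similar for categorical variables.

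SAP 7.1 calls for tabulations by arm and quarter, which go into the closed report while the study runs. The descriptive part of SAP 7.5.1 adds: "The number of participants with any bacterial STI, and with each type of STI, will be summarized at each scheduled visit by arm". Neither place says whether the base is women randomised, women attending or women tested.

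The only missing-data rule, in SAP 5.3.1, is confined to the main analysis: "Complete case analysis will be used for the primary efficacy analysis". That analysis estimates relative risks over the four visits "using a modified Poisson model fitted using GEE methods to account for repeated observations from each participant".

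SAP 9.2 compares the percentage of participants with doxycycline detected in hair between arms, by quarter. It assays all follow-up samples in the dPEP arm but only a 10% subset of follow-up samples in the standard-of-care arm.

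For gonorrhoea, SAP 7.7.1 says that resistance tabulations "will be reported at baseline, 3, 6, 9 and 12 month visits in GC cases in each arm", yet lists the categories as "Tabulations of resistance (No GC, GC: TNC resistance testing = missing, not resistant, resistant".

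**The concern.** A woman who misses a visit, or whose sample is not assayed, has no result. If she stays in the denominator and cannot enter the numerator, the table counts her as negative. Three things follow.

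- The by-visit STI percentages would be too low and would not match the complete-case model reported beside them.
- In an open-label trial, attendance may differ by arm. If it does, the raw contrast between arms shifts for reasons unrelated to infection. The monitoring board would see this in the closed report.
- In SAP 9.2 the two arms are assayed at very different rates by design. A common rule that divides by the whole arm would shrink the control-arm figure about tenfold and leave the dPEP figure nearly intact. That figure is the plan's direct evidence on contamination.

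**Working it through.** **Inputs from the documents.** SAP 3.3.1: 223 per arm, 22% versus 11% over one year, 10% loss to follow-up. SAP 9.2: 10% of control-arm follow-up samples assayed. Protocol Table 3: gonorrhoea incidence 11% to 20% per year across the three cohorts. Protocol section 1.0: tet(M) in 48/50 = 96% of gonorrhoea samples.

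**Assumptions.** Constant risk per quarter; missed-visit shares by arm; number of control-arm women assayed in a quarter and number positive. The documents give none of these.

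**The plan's own figures.** 223 × 0.9 × 0.22 = 44.2 and 223 × 0.9 × 0.11 = 22.1, which match the stated 44 and 22 cases. The arm size of 223 is therefore used below. (The Protocol's statistical section gives 275 per arm. The shrinkage factors below do not depend on arm size.)

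**By-visit STI percentages.**

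- Quarterly risk among tested women: 1 − (1 − 0.22)^0.25 = 6.0% in control and 1 − (1 − 0.11)^0.25 = 2.9% in dPEP; ratio 0.0287/0.0602 = 0.48.
- With the whole arm as base and a share m missed, the percentage shown is p × (1 − m). The ratio shown is 0.477 × (1 − m_dPEP)/(1 − m_SOC).

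| Missed, SOC / dPEP | Shown, SOC | Shown, dPEP | Ratio shown |
|---|---|---|---|
| none | 6.0% | 2.9% | 0.48 |
| 10% / 10% | 5.4% | 2.6% | 0.48 |
| 5% / 15% | 5.7% | 2.4% | 0.43 |
| 15% / 5% | 5.1% | 2.7% | 0.53 |

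**Control-arm doxycycline detection (SAP 9.2).** If the 10% subset means about 223 × 0.10 ≈ 22 women in a quarter, and 5 are positive (assumed), then 5/22 = 23% among those assayed. With the whole arm as base it is 5/223 = 2.2%. The factor is the share assayed, about 0.10. The hair population in SAP 5.2.6 covers only the dPEP arm, so no defined population supplies another base for the control arm.

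**Gonorrhoea resistance (SAP 7.7.1).** The text restricts the table to gonorrhoea cases, but a No GC row belongs only in a whole-arm table. To see what depends on this: at 11% to 20% per year and 10% missed, there are 223 × 0.9 × 0.0287 = 5.8 to 223 × 0.9 × 0.0543 = 10.9 cases per arm per visit. With 96% carrying tet(M), the share is 96% of cases but 2.5% to 4.7% of the arm. If dPEP halved gonorrhoea and left resistance among cases unchanged, the arm-based figure would fall to 1.2% to 2.3% while the case-based figure stayed at 96%.

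**The case against.** The strongest reply is that 5.1 is a formatting convention. Its example is a baseline variable, for which the whole arm is the natural base, and specific text should govern over general text. The by-visit STI text in 7.5.1 speaks of numbers of participants, not percentages. The CONSORT diagram (SAP 6.1) will show retention by visit, and SAP 9.3 reports incidence rates separately. With equal attendance the ratio between arms does not move, and the documents assume no difference in attendance.

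Much of this stands. A reader might infer that every percentage in the report is wrong, or that resistance will not be reported among cases. The documents do not support that. Chlamydia resistance is tabulated among chlamydia cases (7.7.2), gonorrhoea resistance is said to be among gonorrhoea cases (7.7.1), calendar-based coverage is limited to women reporting sex (8.5.1), and symptom status is a proportion of STIs (9.4). Each sets its own base. The No GC row leaves the gonorrhoea table unclear; it does not settle it as a whole-arm table.

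What does not stand is that nothing needs changing. 5.1 says categorical summaries carry both counts and percentages, so percentages are to be expected beside the visit counts. No section gives a tested-at-visit base, and the appendix for data-report contents (11.1) is still to be completed. For 9.2 the text does specify percentages, and incomplete assay is part of the design.

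**Conclusion.** The point holds for two sets of tables: the by-visit STI percentages and the control-arm detection percentage in 9.2. Taken literally, 5.1 gives wrong figures there and no other text corrects it. In the first the understatement equals the share of visits missed (6.0% shown as 5.4% at 10%). The ratio between arms is distorted only under differential attendance (0.48 to 0.43 or 0.53 at 5% versus 15%). In the second the figure shrinks about tenfold (23% to 2.2% in the assumed example). Attendance, the number of women assayed and the number positive are all assumptions.

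A reader might also infer that the efficacy result is biased by this rule. It is not: the primary relative risk, its confidence interval and its test rest on complete cases, and the resistance regressions are fitted to cases. The problem is confined to descriptive tables and is worth correcting before database lock.

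**What to change.** Amend SAP 5.1: baseline percentages use all subjects in the arm; every other percentage uses the participants (or samples) with a non-missing result for that item at that visit, or the base named in the relevant section; each cell shows n/N, and the number missing is given. For STI tables, the result for a visit should be the one assigned to it under 7.5.1, including infections carried forward from interim visits, so that table and model agree.

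In 7.7.1, reconcile the No GC row with the restriction to gonorrhoea cases. Report resistance among cases with a resistance result, at baseline and follow-up, and show untested cases separately. The populations in 5.2.4 and 5.2.5 are post-baseline only, so they cannot serve as the base for the baseline columns in 7.7.

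In 9.2, use participants with assayed hair as the denominator in each arm.

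Leave 9.4 as a proportion of STIs. Population 5.2.7 should not be its denominator: it contains only asymptomatic infections, so the asymptomatic share would be 100% by construction.

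The cost is one revised sentence in 5.1 and short clarifications in 7.7.1 and 9.2. No new data are needed, and no estimate, test or sample-size figure changes.

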### **5.2. Analysis Populations**

#### **5.2.1. Screened population**

All subjects who give informed written consent for screening but are not enrolled will be characterized based on reason for screen failures (e.g., lost-to-follow-up, did not meet entry criteria, administrative) in summary tables. These subjects will neither contribute to other data presentations nor participate in formal analyses.

#### **5.2.2. ITT Population**

The intent to treat (ITT) population comprises all randomized participants.

#### **5.2.3. dPEP Safety Population for dPEP**

The ‘Safety Population’ is defined as all subjects who were dispensed at least one dose of study medication. This population is expected to be identical to participants randomized to dPEP for this study.

#### **5.2.4. GC positive Population**

Post-baseline GC positive participants assessed for TCN resistance. All participants with positive GC will be assessed for molecular resistance

#### **5.2.5. CT positive Population**

Post-baseline CT positive participants assessed for TCN resistance. All participants with positive CT will be assessed for molecular resistance

#### **5.2.6. Hair population**

Participants in the dPEP arm who have hair assessed for quantitative PK assays.

#### **5.2.7. Asymptomatic STI population**

Participants who have tested positive for an STI (CT, NG, and/or TP) and “Per national guidelines, do abnormal findings require immediate STI treatment?” is answered “no”

#### **5.2.8. SMS responder population**

Participants who have responded to at least 4 SMS surveys

### **5.2.9. Subgroups**

The following subgroups will be defined by baseline characteristics

- Age:  $\leq$  vs  $> 24$  years old at enrollment
- Nulliparous: No previous live births
- Using contraceptives: IUD, implants, DMPA, oral contraceptives
- Any STI at baseline: Any laboratory confirmed diagnosis of GC, CT or incident syphilis during enrollment visit(s).
- Transactional sex: exchanged sex for goods, services, or money in the last 3 months

## **5.3. Handling of Missing Data**

### **5.3.1. Missing Efficacy Endpoints**

Complete case analysis will be used for the primary efficacy analysis

## **6. STUDY POPULATION**

### **6.1. Participant Disposition**

A consort diagram will describe the number screened, randomized, retained by visit, and contributing to the primary analysis endpoints by arm. Reason for screen-out and non-inclusion in the primary outcome will be summarized.

### **6.2. Screen Failures**

Reason for screen failures will be summarized by arm

### **6.3. Protocol Deviations**

A listing or summary of major protocol deviations will be provided

